Serum Levels of C Type Natriuretic Peptide in Different Reproductive Periods

NCT04000815

Date:21.01.2020

Serum Levels of C Type Natriuretic Peptide in Different Reproductive Periods

NCT04000815

Date:21.01.2020

Study Protocol and Statistical Analyses Plan

Recent studies have shown that C type natriuretic peptide (CNP) that is produced from granulosa cells of the ovary, has an increasing effect on cyclic guanosine monophosphate (cGMP) production by affecting cumulus cells through natriuretic peptide receptors (NPR). It has been suggested that the transport of cGMP to oocyte via gap junctions causes an inhibition on oocyte phosphodiesterase 3 which leads an increase in cyclic adenosine monophosphate (cAMP) levels within the oocyte by hydrolyses. An important role of increased cAMP levels in oocyte is shown to suppress meiotic progression. Hormonal regulation of CNP secretion has been demonstrated in animal and human studies. Deoxyribonucleic acid (DNA) studies in animals have shown that expression of the natriuretic peptide precursor (NPPC) increases during the periovulatory period and shows that this increase decreases rapidly after Luteinizing hormone(LH) / human chorionic(hCG) stimulation. Human studies have shown that after ovulation induction, the CNP level in follicular fluid decreases following ovulatory dose of hCG. It has been demonstrated by many studies that LH has a suppressing effect on NPPC / NPR2 production. In other studies, estradiol has been shown to have a promoting effect on NPPC. Follicle stimulating hormone (FSH) alone, has been shown to have no effect on CNP regulation. In fact when there is estrogenic effect together with FSH, there is increasing CNP levels.

C type natriuretic peptide, which has been demonstrated that is affected by E2, LH and FSH in the hormonal regulation and is synthesized by the granulosa cells, may be a new ovarian reserve test. And also, it may be associated with increased age, which is also an important factor in ovarian aging. In this study, it was aimed to determine and to compare serum CNP values in three different stages of reproductive life.

In this prospective study, 71 patients are recruited. After the exclusion of patients, group 1 consists of 15 healthy reproductive aged women between 18-40 years old, with regular menstruation. Group 2 includes 15 patients in perimenopausal time period between 40-49 ages and in group 3 there is 15 postmenopausal women.

Age, gravida, parity and body mass index (BMI) data of all patients are recorded. BMI is calculated by dividing the body weight in kilograms by the square of the height in meters. All patients went under ultrasound examination by the same clinician ([name]). The number of antral follicles in group 1 and group 2 were recorded. In addition, on the 2nd or 3rd day of menstruation, serum FSH, LH and E2 data of the patients in group 1 and 2 were recorded.

Patients with drug use that may affect menstruation like oral contraceptives in the last 6 months, patients with a known cardiac or renal disease and therefore using medicine, patients

Serum Levels of C Type Natriuretic Peptide in Different Reproductive Periods

NCT04000815

Date:21.01.2020

suffering from infertility as a result of any reason other than unexplained etiology, patients with a history of ovarian surgery, presence of polycystic ovary syndrome or that have an irregular menstrual cycle were excluded from this study. In addition, patients with central nervous system and endocrine diseases were excluded.

Morning fasting venous blood samples were taken from the patients on the 2nd or 3rd day of the menstruation for group 1 and 2. All blood samples were centrifuged on the day of collection and separated serum samples and were kept at -80 degrees celcius until the day of CNP test. Serum CNP levels of the patients were analyzed by an enzyme-linked immunosorbent (ELISA) assay for human CNP in accordance with the manufacturer's instructions (SEA721Hu, ELISA Kit for Human CNP, Wuhan USCN Business Co., Ltd., Cloud-Clone Corp., CCC, USA).

Data were analyzed using Statistical Package for Social Sciences software (SPSS v15, SPSS Inc, Chicago, IL, USA). The variables were investigated using visual and analytical methods (histograms, homogeneity of variances test, Kolmogorov-Simirnov/Shapiro-Wilk's test) to determine whether or not they were normally distributed. Patient demographics and CNP values were presented as median and interquartile range. Gravida and parity were demonstrated by frequency distribution. The correlation coefficients and their significance were calculated using the Spearman test. P-values less than 0.05 will be regarded as statistically significant.

Results

A total of 45 patients were evaluated in the statistics. The flow chart of the study is shown in figure 1. Table 1 shows the demographic characteristics and table 2 shows frequency distribution of gravida and parity of the patients. In table 3 serum CNP levels are shown. The median and interquartile range of serum CNP levels in groups 1, 2 and 3 were, 43.68 (35.54-47.87) pg/mL, 55.98(49.84-61.13) pg/mL and 116.36(59.61-250.00) pg/mL, respectively. When the three groups were compared with Kruskal Wallis test, there was a significant difference between them in terms of serum CNP values ($p<0.001$). Post hoc analysis showed significant differences between group 1 vs. group 2, group 1 vs. group 3 and group 2 vs. group 3. (p values; $p <0.001$, $p <0.001$, and $p = 0.002$, respectively). When all patients were evaluated, a positive correlation was found between age and serum CNP levels. ($R_s= 0.712$, $p<0.001$) (Figure 2) In group 1 and group 2, there was a positive correlation between serum CNP and serum FSH, ($R_s=0.609$, $p<0.001$) (Figure 3) and a negative correlation between serum CNP and AFC. ($R_s= -0.603$, $p<0.001$) (Figure 4) There was no correlation between serum CNP and serum LH and E2 values in group 1 and 2.

Figure 1: Flow chart of the study

Serum Levels of C Type Natriuretic Peptide in Different Reproductive Periods

NCT04000815

Date:21.01.2020

[figure not shown]

Table 1. Demographic characteristics of participants

	Group 1(n=15)	Group 2 (n=15)	Group 3 (n=15)	All participants (n=45)
Age (years)	24.9±2.9	44.1±2.2	57.7±5.4	42.2±14.1
BMI (kg/m ²)	21.3±1.9	24.3±2.4	27.1±4.1	24.2±3.8
AFC	14.2±2.18	8.33±1.72	-	11±7
FSH (mIU/mL)	5.28±1.33	13.12±7.3	-	7.65±7.96
LH(mIU/mL)	5.71±2.51	5.16±2.45	-	5.29±2.76
E2(pg/mL)	41±26	22±14	-	32±27

BMI: Body mass index, AFC: Antral follicle count, FSH: Follicle stimulating hormone, LH: Luteinizing hormone, E2: Estradiol

Table 2: Frequency distribution of gravida and parity among groups

Frequency	Group 1 (n=15)		Group 2 (n=15)		Group 3 (n=15)	
	Gravida	Parity	Gravida	Parity	Gravida	Parity

Serum Levels of C Type Natriuretic Peptide in Different Reproductive Periods

NCT04000815

Date:21.01.2020

0	14	14	1	1		
1	1	1	1	4		1
2			8	8	5	10
3			4	2	4	2
4			1		3	1
5					1	
7						1
10					2	

Table 3. Serum CNP levels of participants

	Group 1(n=15)	Group (n=15)	Group 3 (n=15)	p
CNP (pg/mL)	43.68 (35.54-47.87)	55.98(49.84-61.13)	116.36(59.61-250.00)	<0.001

CNP:C type natriuretic peptide

Group 1 vs group 2: **p<0.001**; group 1 vs group 3: **p<0.001**; group 2 vs group 3: **p=0.002**.

Figure 2. Correlation between age and serum CNP

Serum Levels of C Type Natriuretic Peptide in Different Reproductive Periods

NCT04000815

Date:21.01.2020

[figure not shown]

Figure 3. Correlation between serum CNP and serum FSH

Serum Levels of C Type Natriuretic Peptide in Different Reproductive Periods

NCT04000815

Date:21.01.2020

[figure not shown]

Figure 4. Correlation between serum CNP and AFC

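### Does the lack of a printed criterion for perimenopause, beside an irregular-cycle exclusion with no stated scope, undermine the contrasts that use group 2?

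*Combined protocol and SAP*

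**What the plan says.** The combined protocol and SAP has no numbered sections. The opening narrative gives the aim, which is to determine serum CNP and "to compare serum CNP values in three different stages of reproductive life", and then describes the groups:

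- Group 1: "group 1 consists of 15 healthy reproductive aged women between 18-40 years old, with regular menstruation".
- Group 2: "Group 2 includes 15 patients in perimenopausal time period between 40-49 ages".
- Group 3: postmenopausal women, again 15, with no criterion printed for that term either.

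The exclusion paragraph lists, among other reasons, "presence of polycystic ovary syndrome or that have an irregular menstrual cycle were excluded from this study". It names no group as covered or exempt.

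Three other sentences bear on group 2. On sampling: "Morning fasting venous blood samples were taken from the patients on the 2nd or 3rd day of the menstruation for group 1 and 2". On hormones: "serum FSH, LH and E2 data of the patients in group 1 and 2 were recorded". On ultrasound: "The number of antral follicles in group 1 and group 2 were recorded". FSH, LH, E2 and antral follicle count are therefore data collected in groups 1 and 2. They are not stated as entry criteria.

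**The concern.** The aim is framed by reproductive stage, and group 2 is the middle stage in two of the three post hoc comparisons. If its stage is not defined, a reader may doubt what those two comparisons show.

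The exclusion sharpens the doubt. Other sentences in the same part of the document name groups 1 and 2 when they are limited to them, and the exclusion does not. Taken at face value it removes women with irregular cycles from the whole study. Group 2 would then be regularly menstruating women aged 40-49, and the printed rules would separate it from group 1 only by age band, the word healthy (used for group 1 alone) and an undefined term. Group 1 against group 2 would be an age contrast under a stage label, and the middle point of the three-stage comparison would be insecure.

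**Working it through.** No design calculation is stated, so there is no planned figure to reproduce. The check sets the sentences side by side and asks what differs between readings.

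**1. Scope of the exclusion.** Postmenopausal women have no menstrual cycle to be regular or irregular, so the rule has no content in group 3. The sentence was evidently not drafted with all three groups in mind. Two readings remain.

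| | A: covers groups 1 and 2 | B: covers group 1 only |
|---|---|---|
| Group 1 | regular cycles | regular cycles |
| Group 2 | regular cycles, age 40-49 | menstruating, age 40-49, regular or not |
| Group 3 | postmenopausal | postmenopausal |
| Irregular cycles in group 2 | 0 of 15 | 0 to 15 of 15 |

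The group descriptions require regular menstruation of group 1 alone. That would be redundant under A, so B is at least as natural. The text does not settle it.

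**2. Is there a contradiction under A?** Only if perimenopause means a change in cycle pattern. The document does not define it that way, and its wording can be read as an age-defined period. With an age-based or reserve-based meaning, the two sentences are compatible.

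**3. What happens to each comparison (Results and Table 3).**

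- 1 vs 2: 55.98 − 43.68 = 12.30 pg/mL, ratio 55.98/43.68 = 1.28, p<0.001. The women compared and the numbers are the same under A and B. Only the description of group 2 differs. The mean ages in Table 1 differ by 44.1 − 24.9 = 19.2 years, so this is also an age contrast on either reading.
- 2 vs 3: 116.36 − 55.98 = 60.38 pg/mL, ratio 116.36/55.98 = 2.08, p=0.002. Group 2 was sampled on day 2 or 3 of menstruation, so under both readings this compares menstruating women aged 40-49 with postmenopausal women.
- 1 vs 3: p<0.001. Group 2 does not enter.

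**4. Do the data suggest a mislabelled middle group?** Central values from Table 1, group 2 minus group 1:

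- FSH: 13.12 − 5.28 = +7.84 mIU/mL
- Antral follicle count: 8.33 − 14.2 = −5.87
- E2: 22 − 41 = −19 pg/mL

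The higher FSH and lower follicle count fit lower ovarian reserve in group 2. I use central values only, because the spreads in these rows are of uncertain type. Read as mean ± SD with n = 15 + 15, FSH recombines to mean (5.28 + 13.12)/2 = 9.20. The sum of squares is 14 × (1.33² + 7.3²) + 30 × 3.92² = 770.8 + 461.0 = 1231.8, and the SD is √(1231.8/29) = 6.52. The printed all-participants entry is 7.65 ± 7.96. That mismatch is a separate matter and is used here only to limit what is claimed.

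**5. Analyses that do not use the label.** The correlations of CNP with age (0.712, all patients), FSH (0.609) and antral follicle count (−0.603, both in groups 1 and 2) use individual values. They depend on who was recruited, but not on what group 2 is called.

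**The case for a change.** The strongest opposing case is that the finding needs no outside definition of perimenopause. Whatever the term means, the document does not say how a woman was judged to be in that stage, and two plausible scopes of the exclusion give two different populations for group 2. FSH and follicle count were measured, not used for entry, and age alone could produce the differences in Table 1. They show a lower average reserve without showing how any individual was classified. Stating the criterion and the scope would cost a sentence or two.

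Much of this stands: the criterion is unwritten, the scope is unwritten, and Table 1 cannot replace either. It does not show that following the plan gives a wrong result. Writing down what was done would leave every estimate, test and p-value as it is. Nor is the gap peculiar to group 2, since the label for group 3 is equally undefined.

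The 26 of 71 recruited women who were not analysed (71 − 45; 36.6%) add nothing. The text refers to a flow chart, Figure 1, which was not visible in the copy read and may give the reasons. The lack of a breakdown in the text is not evidence of a gap.

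**Conclusion.** The concern does not call for a change to the plan. It identifies a missing detail: how perimenopausal status was judged, and which groups the irregular-cycle rule covered. Its reach is mainly the description of one comparison, group 1 against group 2. If group 2 was limited to regular cycles with no other criterion, that comparison is best described as one between regularly menstruating women of different ages and ovarian reserve. Group 2 against group 3 keeps essentially the same meaning on both readings, and group 1 against group 3 is untouched. The size of the effect on the reported numbers is zero: no median, p-value or correlation changes.

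This rests on three assumptions: that the exclusion was not meant to act in group 3, that group 2 women were menstruating as the sampling sentence implies, and that the central values in Table 1 are correct as printed. If the study records showed that group 2 was assembled by some rule inconsistent with its printed age band or with cycle-day sampling, the point would need to be reopened. Nothing in the document suggests that.

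### The all-patient age-CNP correlation (Rs = 0.712) is fully consistent with the three-group gradient alone and is not separate evidence that CNP is associated with age

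*Combined protocol and SAP*

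**What the plan says.** The combined protocol and SAP has one stated aim: to compare serum CNP across three stages of reproductive life. The rationale adds an idea about age, that CNP "it may be associated with increased age, which is also an important factor in ovarian aging".

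The groups are set out in the design paragraph: "group 1 consists of 15 healthy reproductive aged women between 18-40 years old, with regular menstruation", then "Group 2 includes 15 patients in perimenopausal time period between 40-49 ages and in group 3 there is 15 postmenopausal women". Group 3 has no stated age limits.

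On correlation the statistical paragraph says only: "The correlation coefficients and their significance were calculated using the Spearman test". It describes no stratified, partial or stage-adjusted analysis.

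The Results report the Kruskal-Wallis test (p<0.001) and three pairwise comparisons (group 1 vs 2 p<0.001, 1 vs 3 p<0.001, 2 vs 3 p=0.002). They then state: "When all patients were evaluated, a positive correlation was found between age and serum CNP levels", with Rs = 0.712, p<0.001 and a reference to Figure 2. The text and tables give no age-CNP coefficient within any group.

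**The concern.** The age correlation is printed after the group comparison with its own coefficient, p-value and figure, and without a caveat. A reader may count two findings: CNP differs by reproductive stage, and CNP rises with age. But age in this sample is almost fixed by group. When CNP differs between groups that are ordered by age and well separated in age, a rank correlation over all women comes out strongly positive whatever happens inside the groups.

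What is at stake is the age idea in the rationale. If 0.712 is taken as support for it, the same gradient is used twice. The stage comparison, which is the stated aim, is not affected numerically.

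**Working it through.** **Inputs.** Table 1 ages: 24.9±2.9, 44.1±2.2, 57.7±5.4; all participants 42.2±14.1; n = 15 per group. Results: Rs = 0.712 and the pairwise p-values above. Table 3: CNP median and quartiles 43.68 (35.54-47.87), 55.98 (49.84-61.13) and 116.36 (59.61-250.00) pg/mL. Rs itself cannot be recomputed without patient-level data.

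**1. Reproduce the printed figures.**
- Overall mean age = (24.9 + 44.1 + 57.7)/3 = 42.23.
- Within-group SS = 14 × (2.9² + 2.2² + 5.4²) = 14 × 42.41 = 593.7.
- Between-group SS = 15 × Σ(group mean − 42.23)² = 4506.7 + 52.3 + 3588.3 = 8147.2.
- Overall SD = √[(593.7 + 8147.2)/44] = 14.09.

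These match 42.2±14.1. For the correlation, t = 0.712 × √[43/(1 − 0.712²)] = 6.65 on 43 df, p = 4 × 10⁻⁸, which agrees with p<0.001.

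**2. How much of age is group?**
- Between-group share of age variance = 8147.2/8740.9 = 93.2%. The pooled within-group SD is √(42.41/3) = 3.76 years, against 14.1 overall.
- On ranks, if ages do not overlap, the group mean ranks are 8, 23 and 38, with variance (15² + 0 + 15²)/3 = 150. The total rank variance is (45² − 1)/12 = 168.67, so the between-group share is 150/168.67 = 88.9%.
- If ages are normal within group, a random group 1 woman is older than a random group 2 woman with probability below 10⁻⁶. A random group 2 woman is older than a random group 3 woman about 1% of the time.

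**3. Rs implied by group membership alone.** Let Aij be the probability that a woman in the later group j has higher CNP than a woman in group i. With no age-CNP relation inside any group and no age overlap, the expected value is

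Rs ≈ 75 × (2·A13 + A12 + A23 − 2)/168.67.

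The post hoc test is not named, so I read the p-values as two-sided, unadjusted Mann-Whitney tests. With 15 per group, U has mean 112.5 and SD √(225 × 31/12) = 24.11.
- p = 0.002 corresponds to U = 38, so A23 = 1 − 38/225 = 0.831.
- p<0.001 requires U ≤ 33, so A12 and A13 are at least 1 − 33/225 = 0.853.
- Lower end: 75 × (3 × 0.853 + 0.831 − 2)/168.67 = 0.62.
- Upper end (A12 = A13 = 1): 75 × (3 + 0.831 − 2)/168.67 = 0.81.

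If the printed p-values had instead been multiplied by three (Bonferroni), the limits would be U ≤ 25 for groups 1 vs 2 and 1 vs 3, and U of 30 or 31 for groups 2 vs 3. The range becomes 0.68 (U = 25, 25, 31) to 0.83 (U = 0, 0, 30). Both ranges contain 0.712.

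**4. Simulation with no age effect inside any group.** Ages were drawn from Table 1, and CNP was drawn independently of age within group.

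| CNP model | Conditioned on pairwise p-values | Mean Rs | 95% range |
|---|---|---|---|
| Quartiles fixed as 4th, 8th, 12th ordered values | no | 0.73 | 0.60-0.84 |
| Same | yes | 0.75 | 0.66-0.82 |
| Split-lognormal or split-normal fitted to quartiles | no | 0.56-0.60 | about 0.27-0.82 |
| Split-lognormal | yes | 0.69 | 0.60-0.80 |

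Other runs that kept the quartiles and conditioned on the p-values gave means of 0.72 to 0.73. The printed 0.712 lies inside every range.

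**5. Does 0.712 tell us about age within stage?** In a split-lognormal run without conditioning, moving the true within-group correlation from −0.5 to +0.5 moved the expected overall Rs only from 0.49 to 0.71. The 95% ranges overlap widely (0.21-0.75 and 0.47-0.88).

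**The case against.** The strongest reply is that the document does not overclaim. Its stated aim is the stage comparison, and age is a remark in the rationale. The Results sentence is a true marginal description that nowhere says the correlation is independent of stage. This stands. The point is about what the coefficient can support, not about a false statement.

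A reader might infer from the arithmetic that age and stage cannot be separated at all, or that 0.712 is produced by stage alone. The documents support neither reading. About 7% of the age variance is within groups, so a within-stage estimate can be computed. The stage-only expectation depends on the assumed CNP shape: without conditioning on the p-values it averages 0.56 to 0.60 under one model, and there an overall Rs of about 0.71 is what a within-stage correlation of +0.5 would give on average. A real association within stage is not excluded.

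Nor should the age gaps be put down to the planned bands. The 18-40 and 40-49 bands abut and group 3 is defined by menopausal status. The gaps are in the women enrolled.

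The within-group estimates also have limits. Age within a group may still track reproductive ageing, for example time since menopause. Stage may also lie on the path from age to CNP, so conditioning on it answers a narrower question than whether CNP and age are associated. A null stratified result therefore should not decide whether the marginal association may be reported.

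**Conclusion.** The concern holds in this form: the all-patient Rs of 0.712 is fully consistent with the group gradient already tested by Kruskal-Wallis, and it is not separate evidence for an age association. The size is clear: 93% of age variance is between groups, group membership alone implies an Rs of about 0.62 to 0.81, and conditioned stage-only simulations average 0.69 to 0.75.

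This rests on Mann-Whitney post hoc tests, approximately normal ages within group (with group 3 ages limited to an assumed 45-80 years in the simulations in the table), and assumed CNP shapes between the printed quartiles. Figure 2 was not available and may show the within-group pattern. The stage comparison stands as a description of strata that differ in both age and stage.

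**What to change.** - Keep Rs = 0.712 as a marginal description, and add that it largely reflects the same gradient as the three-group comparison.
- Report the age-CNP Spearman coefficient with a 95% confidence interval within each group, and one group-stratified coefficient (ranks taken within group, then pooled) with a 95% confidence interval. Label all of them descriptive.
- Do not describe age as associated with CNP apart from reproductive stage on the strength of the all-patient coefficient. Describe the group differences as differences between age/stage strata.

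The cost is one run on ages and CNP values already recorded, and a few reworded sentences. The drawback is imprecision. At n = 15, p<0.05 needs |Rs| of about 0.51 (2.16/√(2.16² + 13)). The pooled estimate has 80% power only for a true correlation of about 0.42 or more (tanh[2.80/√40]), and a single group needs about 0.67 (tanh[2.80/√12]). A null result would not show that there is no age association, and the text should say so.

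### The statement that CNP is not correlated with E2 or LH has no coefficient or interval and says more than 30 women can show; for E2, pooling two groups could also hide a positive relation

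*Combined protocol and SAP*

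**What the plan says.** The document is a combined protocol and SAP with results. Its stated aim is descriptive: "it was aimed to determine and to compare serum CNP values in three different stages of reproductive life". The statistical paragraph before the Results heading gives one method for associations, "The correlation coefficients and their significance were calculated using the Spearman test", and one criterion, "P-values less than 0.05 will be regarded as statistically significant". It mentions no stratified or partial correlation, no power calculation and no equivalence bound.

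Hormones were recorded in groups 1 and 2 only, with 15 women in each. For these groups the Results report "In group 1 and group 2, there was a positive correlation between serum CNP and serum FSH" (Rs = 0.609, p<0.001) and "a negative correlation between serum CNP and AFC" (Rs = -0.603, p<0.001). The next sentence is "There was no correlation between serum CNP and serum LH and E2 values in group 1 and 2". It gives no Rs, p-value or interval for either hormone.

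**The concern.** A non-significant test in a small sample does not show that a correlation is absent, and without a coefficient and interval the reader cannot see what the data leave open. The background paragraph describes estradiol as promoting, and LH as suppressing, the CNP system. A flat negative therefore reads as evidence against the study's own rationale.

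E2 raises a second issue. The two groups differ in both variables, in opposite directions. A coefficient computed over both groups mixes the between-group shift with any within-group relation. If the within-group relation were positive, the two parts would tend to cancel.

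**Working it through.** **1. Were the groups pooled?** The printed FSH and AFC results can be checked with t = r·√((n−2)/(1−r²)), two-sided.

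| Result | n = 30 | n = 15 |
|---|---|---|
| FSH, 0.609 | t = 4.06, p = 0.0004 | t = 2.77, p = 0.016 |
| AFC, -0.603 | t = 4.00, p = 0.0004 | t = 2.73, p = 0.017 |

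The printed p<0.001 fits only the pooled 30. E2 and LH are reported for the same groups in the next sentence, so pooling is likely there too, but it is not stated.

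**2. What a non-significant result leaves open.** The critical value is t/√(df + t²), with df = n−2 and two-sided 0.05 (sidedness is not stated). The 95% interval at an observed Rs of 0 is ±tanh(1.96·√(1.06/(n−3))).

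- n = 30: 2.048/√(28 + 2.048²) = 0.361; interval ±tanh(0.388) = ±0.37.
- n = 15: 2.160/√(13 + 2.160²) = 0.514; interval ±tanh(0.583) = ±0.52.

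The same approximation gives power at n = 30 of about 35% for a true Rs of 0.3 and 79% for 0.5.

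**3. Direction of the group shift.** Median CNP goes from 43.68 to 55.98 pg/mL (Table 3; group 1 vs group 2 p<0.001). E2 goes from 41±26 to 22±14 pg/mL (Table 1). The between-group part of a pooled E2–CNP coefficient is therefore negative. LH hardly moves (5.71 to 5.16 mIU/mL).

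**4. Size of the effect on a pooled E2 test.** Simulation with 15 + 15 women, a Gaussian copula with a set within-group Spearman, and 10,000 runs per setting.

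- Hormone normal or log-normal.
- The ± in Table 1 read as mean/SD or as median/IQR width, because the methods promise median and IQR.
- CNP built from the published quartiles in three ways (symmetric, split-normal, log-split).

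That makes 2 × 2 × 3 = 12 readings; the ranges below run over all of them. The stratified test is Spearman on ranks taken within each group (27 df, critical value 0.367).

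| Within-group Rs | Pooled, non-significant | Pooled, significantly positive | Stratified, significant |
|---|---|---|---|
| 0 in both | 45–74% | about 0% | about 5% |
| +0.3 in both | 83–95% | 0.1–1.4% | 32–34% |
| +0.5 in both | 92–97% | 0.4–7% | 75–77% |
| +0.5 in one, 0 in the other | 77–94% | 0.0–1.3% | 22–23% |

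With no within-group relation the mean pooled Rs is -0.24 to -0.37. Depending on the reading, it comes near zero at a within-group Rs of roughly +0.4 to +0.6. For LH with no relation the mean pooled Rs is only -0.06 to -0.10.

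**5. If the tests were run per group (n = 15).** With Rs = +0.5 in both groups each test has 47% power, so neither is significant in 0.53² = 28% of datasets. With +0.3 in both, neither is significant in 66%.

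**6. The same mechanism for FSH and AFC.** With no within-group relation, the group shifts alone give a mean pooled Rs of +0.36 to +0.54 for FSH (printed 0.609) and -0.49 to -0.57 for AFC (printed -0.603).

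**The case against.** The certain part of this point is a matter of reporting and wording. With p<0.05 as the stated criterion, a reader may take the sentence to mean not significant, and the document has no discussion that uses it as proof of absence. The masking of a positive E2 relation is hypothetical; the background remark about estradiol concerns regulation of the precursor and does not establish a relation with serum E2 on cycle day 2 or 3. A pooled coefficient is a legitimate description of association across stages, and no within-stage question is posed. The stratified test would itself often be inconclusive. The percentages rest on an unclear Table 1: the group values for age and BMI reproduce the all-participants column as means, but E2 (computed 31.5±22.7, printed 32±27) and FSH (9.2±6.5 against 7.65±7.96) do not.

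Much of this is right, and it limits the weight of the point. A pooled non-significant result is also not empty of information. It is about 1.3 to 2 times as likely under the positive scenarios as under none, and it counts against a negative relation: with -0.3 in both groups the pooled test is non-significant in only 8–26% of datasets. But this does not rescue the sentence. The result gives no support for absence over a positive relation, and if anything leans slightly the other way. The missing coefficients and intervals, and the opposing shifts in CNP and E2, do not depend on how Table 1 is read.

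**Conclusion.** The concern holds. For both hormones the data cannot support a statement of absence: at an observed Rs of 0, correlations up to about ±0.37 (pooled) or ±0.52 (per group) remain compatible. This needs no simulation. For E2, conditional on pooling, the group shift biases the coefficient downward relative to the within-group relation in all 12 readings; the exact percentages depend on the reading. For LH the pooling bias is small, and only the missing coefficient and interval matter. It is not claimed that a within-group E2 relation exists. The result is secondary, so the sentence should be corrected, but the main CNP comparison is unaffected.

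**What to change.** State whether the E2 and LH tests were pooled or run per group. For each hormone report the pooled Spearman coefficient with its 95% interval, described as the association across stages, and beside it the group-stratified coefficient (ranks within group, 27 df). Its interval is tanh(atanh(Rs) ± 1.96·√(1.06/26)); simulated coverage was 94.5–95.4% for a common Rs of 0 to 0.6. Give FSH and AFC in the same form, so that all four correlations are read alike. Reword the sentence to say that no correlation was detected, followed by the coefficients and intervals.

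The cost is a short re-analysis of existing data and one changed sentence. The drawback is a less definite statement with wide intervals: tanh(1.96·√(1.06/26)), about ±0.38 at a stratified Rs of 0. The stratified analysis helps clearly only if a moderate relation is shared by both groups; if the relation is small or confined to one group, it may stay inconclusive.
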